1. STUDY OBJECTIVES

The global objective of this study is to establish the safety and investigate the potential treatment effect of an intravenous infusion of HB-adMSC on brain structure, neurocognitive/functional outcomes, and neuro inflammation after traumatic brain injury and/or hypoxic-ischemic encephalopathy in adults.

1.1 Primary Objectives: Determine the safety of HB-adMSC as determined by infusional toxicity of the cell product.

Allogeneic MSCs have been used in numerous oncologic and non-oncologic clinical trials. They have an excellent safety profile that has been described in numerous publications. A recent meta-analysis evaluated 1012 patients with a variety of clinical conditions, and found only transient fever as an adverse event. (Lalu, 2012) However, other publications have raised an issue of a complement mediated induction of coagulation using human cells in vitro. (Moll, 2014) We and others have confirmed these findings, and have noted a Tissue Factor mediated pro-coagulant response associated with various types of MSCs with a wide variability related to CD142 expression. (Mangum, 2017; Christy, 2017, George, 2018) We propose evaluating the potential infusional toxicity of HB-adMSC in patients with sub-acute and chronic neurological injury.

1.2 Secondary Objectives: Obtain treatment effect estimates of HB-adMSC infusion on global gray and/or white matter as well as structural integrity of GM and WM regions of interest in the corpus callosum and corticospinal tracts as measured by fractional anisotropy (FA) and mean diffusivity (MD) in specific regions known to correlate with specific neurocognitive deficits in patients after neurological injury.

We propose to investigate changes (from enrollment to 6 months post infusion) in global measures of structural integrity in GM and WM using volumetric and DT-MRI based imaging according to the protocols described in the appendix/Investigator Brochure. T1-weighted images will be reviewed for image quality prior to performing morphometric analyses. Using Freesurfer v5.0.0 software (www.surfer.nmr.mgh.harvard.edu), each brain is skull-stripped and segmented into 3 classes of voxels: gray matter, white matter, and cerebrospinal fluid (Dale & Sereno, 1993; Dale et al., 1999). Subsequently, the cortex will be parcellated for individual gyri yielding morphometric measures of cortical thickness, volume, and surface area and measures of underlying white matter fractional anisotropy (FA) within each gyrus (Fischl & Dale, 2000).

Further, we will measure white and gray matter regions of interest and will correlate the degree of injury/preservation with functional and neuropsychological outcome measures. These measures have been validated in multiple studies and are recommended by a task force from NIH and NIDRR as common data elements for TBI outcome research (McCauley et al., in press) and for use in clinical trials in TBI (Bagiella, 2011). These measures were also selected to assess relations with specific white and gray matter structures that are particularly vulnerable to disruption by TBI. White matter: corpus callosum (processing speed), corticospinal tract (motor coordination). Gray matter: frontal lobe (fluency, attention, working memory) and temporal lobe (declarative memory).

1.3 Exploratory Objectives: Investigate if HB-adMSC infusion reduces the neuroinflammatory response to injury.

Microglial activation has been shown to occur after TBI and chronic activation is associated with WM loss over time. (Loane, 2014; Ramlackhansingh, 2011). We have confirmed these findings in a rodent model of TBI as well, using both the M1 microglial activation marker, IBA-1 as well as the TSPO ligand, PBR-28. [¹¹C]ER-176 is a Radioligand for the TSPO with adequate sensitivity to robustly image all three affinity genotypes in human brain (Ikawa, 2017). We plan to use the approach to image the neuroinflammatory response to injury. These imaging findings will be correlated with circulating inflammatory cytokines.

7. Concurrent participation in interventional drug or device study.
8. Inability to undergo the diagnostic tests (PET/DT-MRI) or unwilling/unable to cooperate with the diagnostic tests and outcome assessments.
9. Unwilling or unable to return for the follow-up study visits.
10. Individuals planning to receive a vaccination two weeks before the brain imaging visits or planning to receive a vaccination two weeks before or after a stem cell infusion visit.

The exclusion criteria are designed to prevent the enrollment of patients with chronic diseases or pre-existing conditions that would influence the study outcome measures. Also, patients with previous malignancy or immunosuppression are excluded as immunomodulation of the inflammatory response to injury is one of the putative mechanisms of action. Spinal cord injury is an exclusion criterion due to the inability to perform many of the functional outcome measures. Significant pulmonary disease is an exclusion criterion due to the potential for exacerbation of lung dysfunction with the intravenous cell infusion. Lovenox administration for the prophylactic prevention of DVT/PE is contraindicated in individuals with known sensitivity to heparin and pork products, individuals with mechanical

prosthetic heart valves, individuals with spinal deformities, history of spinal cord injury or surgery. Vaccinations are known to produce a temporary systemic inflammatory response that may alter the brain PET scans and inflammatory biomarker results. The effects of concomitant administrant of vaccines and stem cells are unknown.

3.3 Selection and Pre-Screening of Subjects:

Subjects will be recruited from the PI/Co-Investigator clinic population or by self-referral. Potential subjects referred to the study will be contacted by telephone and screened using an IRB approved screening telephone script. The study consent will be mailed to potentially eligible subjects wanting to proceed with the screening visit. Potential subjects may also be identified from the PI/Co-Investigator's clinic population and approached in person during a routine clinic visit. The research staff will screen potential subjects using standard of care medical record information and the inclusion/exclusion criteria listed above.

Subjects may also be recruited from two IRB approved studies, HSC-MS-16-0283 or HSC-MS-15-0744. Potentially eligible subjects will be offered the opportunity of enrolling in the Hope Bio study during the end of study visit for the two protocols listed above. The two studies share the same PET/DT-MRI imaging and analysis procedures as those listed in this protocol. Subjects consenting to enroll in the Hope Bio study will not be required to repeat a brain PET/DT-MRI. Their PET/DT-MRI imaging data from HSC-MS-16-0283 or HSC-MS-15-0744 will be used for the Hope Bio study baseline imaging visit.

During the first visit, the PI/Co-PI will review the study consent with the patient or their LAR. The PI and/or Co-PI will meet with the patient and explain the purpose of the study, study procedures (including the adipose tissue extraction, cell infusions, and safety assessment procedures), follow-up visits, potential risks and benefits of the study, alternatives, and the voluntary nature of participation. Ample time will be given for the patient to ask questions and make a decision about participation. If consent is obtained, a schedule of study events and a copy of the signed informed consent document will be provided to the patient. The informed consent process will be documented in the subject's medical record and will include the discussion points mentioned above. A copy of the signed informed consent will be placed in the medical record. If consent is not obtained from the patient, data collection will cease and the subject deemed a screening failure. A screening log will be maintained to track enrollment information and reasons for screened but ineligible subjects.

Subjects meeting the initial pre-screening interview (either in person or by telephone) will be scheduled for the 1st study visit in the Clinical Research Unit (CRU) at Memorial Hermann Hospital and if eligible, continue on with the study procedures/visits presented in Table 1 below.

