3.4 Visit #1: Screening & Consent

During this visit, and after consent has been obtained, the subject will undergo the following procedures:

1. Medical history including current medications and vaccinations,
2. Physical and neurological exam,
3. Vital signs (Heart Rate, BP, Respirations, Temp., SpO₂),
4. Blood samples for baseline clinical labs (CBC with diff., CMP, coagulation panel, renal function panel, urine hCG if applicable), and neuroinflammatory biomarkers and TSPO genotype,
5. Chest x-ray (AP, single view).
6. Baseline neurocognitive assessments.

The screening visit is anticipated to take about 4hr. to complete. The site PI/Co-PI will make the final determination on the subjects' eligibility and complete the inclusion/exclusion CRF. Ineligible

subjects will be notified by telephone and referred to their PCP for follow-up care if indicated. Subjects meeting study eligibility will be contacted by telephone to schedule the baseline imaging visit. The baseline imaging visit will be completed within 10 days of the screening visit.

Subjects entering the study from HSC-MS-16-0283 or HSC-MS-15-0744 will already be consented and will not have a blood sample drawn for their TSPO genotype.

Subjects will also be referred to a physician with Hope Biosciences who will perform the adipose tissue extraction. The adipose tissue extraction and processing will be performed under Hope Biosciences IND #18388 CMC procedures. Hope Biosciences' SOP for the adipose tissue extraction is provided in Appendix 1. If for any reason Hope Biosciences is unable to prepare the HB-AdMSC infusion (insufficient stem cells, contamination, etc.) the subject will be contacted and given the option to repeat the adipose tissue extraction or withdrawal from participation.

A staggered infusion visit plan for the 1st four subjects is included in Appendix 3

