3.8 Visits #7: One Year Post-Infusion

The one year post-infusion visit will be conducted in the CRU and is expected to take about 2 hours to complete. The visit will include:

1. Interval H&P update,
2. Physical and neurological exam,
3. Vital signs (Heart Rate, BP, Resp., Temp., SpO₂),
4. Blood sample for clinical labs (CBC with diff., CMP, coagulation and renal function panels) & neuro-inflammatory biomarkers,
5. A pregnancy test will be repeated for female subjects of child bearing potential (if applicable),
6. Chest x-ray (AP, single view),
7. Neurocognitive/functional outcome assessments.

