NIH Toolbox – Cognition: Dimensional Change Card Sort Test		
NIH Toolbox – Cognition: Pattern Comparison Processing Speed Test		
Rey Auditory Verbal Learning Test (RAVLT)		
D-KEFS: Verbal Fluency (VF)		
Wechsler Adult Intelligence Scale - IV: Coding (WAIS IV – CD)		
Wechsler Adult Intelligence Scale – IV: Symbol Search (WAIS IV – SS)		

5.3 Cytokines and Pro/Anti-Inflammatory Marker Evaluation:

Plasma cytokines, IL-1 α , IL-4, TNF α , IL-6, IL-10 and albumin will be measured via a bead-based, flow cytometric ELISA for the cytokines, and BCG immunochemical analysis for albumin concentration. Samples will be obtained at the baseline imaging visit #2, and at the 6 and 12 month follow-up visits. This approach is based on findings that cytokine markers may be a useful biological effect marker for Phase 2 and 3 trials.

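### The vaccination window is tied to imaging and infusion visits, not to biomarker draws, so it misses the 12-month draw for everyone and the baseline draw for feeder-study subjects

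*Protocol*

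**What the plan says.** **The rule.** Item 10 of section 3.2, repeated in the synopsis, excludes "Individuals planning to receive a vaccination two weeks before the brain imaging visits". A second limb of the same item deals with the infusions and excludes anyone "planning to receive a vaccination two weeks before or after a stem cell infusion visit". The paragraph after the criteria explains that the systemic inflammation caused by a vaccine "may alter the brain PET scans and inflammatory biomarker results".

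**The draws.** Section 3.4 lists blood at Visit 1 for "neuroinflammatory biomarkers and TSPO genotype", and Tables 1a and 1b also put the baseline biomarker sample at Visit 1. Section 5.3 differs: "Samples will be obtained at the baseline imaging visit #2, and at the 6 and 12 month follow-up visits". Section 3.7 has biomarkers and PET/DT-MRI together at Visit 6. Section 3.8 has "coagulation and renal function panels) & neuro-inflammatory biomarkers" at Visit 7, with no imaging and no infusion.

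**The spacing.** Section 3.4 states: "The baseline imaging visit will be completed within 10 days of the screening visit". Subjects from the two feeder studies reuse their earlier scans (sections 3.3 and 3.5), and their Visit 2 column in Table 1b is empty.

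**The analysis.** Section 8.2.2 of both the protocol and the SAP fits a mixed model to the cytokine time course, with time and GOSE as covariates and a random subject effect. Vaccination is not in the model.

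**The concern.** The rule is narrower than its reason. Two things are to be kept free of vaccine effects, PET scans and inflammatory markers, but only the scans have a window of their own. A biomarker sample is protected only if it happens to fall close to an imaging or infusion visit.

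The trial has one arm, so change from baseline is the only contrast. A marker raised by a vaccine at baseline would look like a later fall, in the direction of benefit. One raised at 12 months would hide a fall or show a rise. No control group shares the disturbance, and the cytokine model has no term for it.

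**Working it through.** The plan gives no figure to reproduce here. The check is how many of the 14 days before each biomarker draw fall inside some item 10 window.

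**Inputs.** Window of 14 days before imaging (Visits 2 and 6) and 14 days either side of each infusion (Visits 3 to 5): section 3.2. Visit 1 to Visit 2 gap of 0 to 10 days: section 3.4. Cell processing of 5 to 7 weeks and a tolerance of +/- 21 days at Visits 6 and 7: Tables 1a and 1b.

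**Visit 1, Table 1a subjects.** The window before Visit 2 reaches back past Visit 1. Days covered = 14 - gap.

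| Gap (days) | Covered | Uncovered |
|---|---|---|
| 0 | 14 | 0 |
| 5 | 9 | 5 |
| 7 | 7 | 7 |
| 10 | 4 | 10 |

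The uncovered days are those furthest from the draw. If the baseline is drawn at Visit 2, all 14 days are covered.

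**Visit 1, Table 1b subjects.** There is no imaging visit in this trial before Visit 6. Taking extraction on the day of Visit 1, infusion 1 comes at about day 35 to 49, so its window opens 35 - 14 = 21 to 49 - 14 = 35 days after the draw. Covered: 0 of 14. Section 5.3 does not help, since these subjects have no Visit 2.

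**Visit 6.** Imaging belongs to the same visit, so the draw is covered.

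**Visit 7.** Days are counted from infusion 3. The last infusion window closes on day 14. Visit 6 falls at the latest on about day 182.6 + 21 = 204. The 14 days before the earliest Visit 7 begin at about 365.25 - 21 - 14 = day 330. No window reaches them. Covered: 0 of 14.

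**Size, on assumptions only.** Mean shift at a draw = share of subjects recently vaccinated x lift in the marker. The documents give neither. Assume one or two vaccinations a year, evenly spread over 26 two-week periods: the share is 1/26 = 3.8% to 2/26 = 7.7%. Assume a lift of 0.5 to 1 SD of the marker. The shift is then 0.038 x 0.5 = 0.02 SD to 0.077 x 1 = 0.08 SD. A share of 10 to 25% would give 0.05 to 0.25 SD, but under even timing it implies 0.10 x 26 = 2.6 to 0.25 x 26 = 6.5 vaccinations per person per year. Seasonal clustering could raise the share for some draws.

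**The case against.** A reader might infer that two of the three biomarker time points, including the baseline, are unprotected for all subjects. The documents do not support that. For Table 1a subjects the 10-day limit brings at least the last 4 days before Visit 1 inside the window, and section 5.3 puts the baseline at a visit that is fully covered. Even so, that protection is incidental. It also requires reading a criterion about planned vaccination as applying to one already given before Visit 1, which the wording leaves open.

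It can also be said that vaccination is already recorded. Section 3.4 lists it at Visit 1, and section 3.6 includes recent vaccinations in the interval update at infusion visits. This stands in part: affected Visit 1 samples could be identified afterwards, so the effect is not beyond separating there. But the lists for Visits 6 and 7 name only an interval update, and no analysis uses the information.

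The two biases oppose each other. If vaccination is equally likely before Visits 1 and 7, they cancel on average in the 12-month change. That could hold for feeder-study subjects. It does not hold where the baseline is better covered than Visit 7, as for Table 1a subjects.

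Finally, item 10 suits Visit 7 poorly, since at enrollment it would ask about plans more than a year ahead. And a vaccination given before consent can only be recorded. Both points stand, and they argue for recording and flagging rather than a wider exclusion.

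**Conclusion.** The point holds in limited form. The Visit 7 draw is outside the rule for every subject, and the Visit 1 draw is outside it for feeder-study subjects. For the rest, the baseline is partly or fully covered, depending on which section governs when it is drawn.

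The impact is small. The markers serve an exploratory objective (section 1.3), section 8.2 reports differences at 6 months, and the Visit 6 sample is covered. The baseline does enter the 6-month change, so feeder-study subjects are not wholly clear there. The documents do not say how many of the 24 they will be.

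The bias cannot be derived from the documents; the 0.02 to 0.08 SD above rests on assumed vaccination rates and marker lifts. Nor should it be set directly against a confidence-interval half-width of about 0.42 (2.069/sqrt(24)). That figure is in SDs of change, which equal SDs of the marker only if the pre/post correlation is 0.5 and the variances are equal. This is a cheap improvement, not a threat to the trial's main conclusions.

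**What to change.** 1. Reconcile section 3.4 and Tables 1a and 1b with section 5.3 on when the baseline biomarker sample is drawn, and state the rule for feeder-study subjects, who have no Visit 2.
2. Record the date of any recent vaccination at every biomarker draw, naming it in the Visit 6 and Visit 7 lists.
3. Where a vaccination falls within the two weeks before a draw, move the research draw, not the vaccination, within the visit window (+/- 21 days at Visit 7). If it cannot be moved, or no window is stated, as at Visit 1, flag the sample.
4. In section 8.2.2 of the protocol and SAP, prespecify a sensitivity analysis of the cytokine model that excludes flagged samples.

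The cost is one CRF question, a few sentences of text and a few rebooked draws. Eligibility and treatment are unchanged.

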3.4 Visit #1: Screening & Consent

During this visit, and after consent has been obtained, the subject will undergo the following procedures:

1. Medical history including current medications and vaccinations,
2. Physical and neurological exam,
3. Vital signs (Heart Rate, BP, Respirations, Temp., SpO₂),
4. Blood samples for baseline clinical labs (CBC with diff., CMP, coagulation panel, renal function panel, urine hCG if applicable), and neuroinflammatory biomarkers and TSPO genotype,
5. Chest x-ray (AP, single view).
6. Baseline neurocognitive assessments.

The screening visit is anticipated to take about 4hr. to complete. The site PI/Co-PI will make the final determination on the subjects' eligibility and complete the inclusion/exclusion CRF. Ineligible

subjects will be notified by telephone and referred to their PCP for follow-up care if indicated. Subjects meeting study eligibility will be contacted by telephone to schedule the baseline imaging visit. The baseline imaging visit will be completed within 10 days of the screening visit.

Subjects entering the study from HSC-MS-16-0283 or HSC-MS-15-0744 will already be consented and will not have a blood sample drawn for their TSPO genotype.

Subjects will also be referred to a physician with Hope Biosciences who will perform the adipose tissue extraction. The adipose tissue extraction and processing will be performed under Hope Biosciences IND #18388 CMC procedures. Hope Biosciences' SOP for the adipose tissue extraction is provided in Appendix 1. If for any reason Hope Biosciences is unable to prepare the HB-AdMSC infusion (insufficient stem cells, contamination, etc.) the subject will be contacted and given the option to repeat the adipose tissue extraction or withdrawal from participation.

A staggered infusion visit plan for the 1st four subjects is included in Appendix 3

3.5 Visit #2: Baseline Imaging

The baseline PET/DT-MRI imaging will be conducted at the Houston Methodist Research Institute (HMRI). The second study visit is expected to take about 5 hours to complete.

Subjects will undergo the following procedures;

1. Interval H&P update,
2. A pregnancy test will be repeated for female subjects of child bearing potential (if applicable),
3. Vital signs (Heart Rate, BP, Resp., Temp., SpO₂),
4. PET/DT-MRI

Subjects and their care providers will receive instructions on administering SQ Lovenox (40mg once a day) for 7 days beginning the day before each infusion visit. Subjects will be asked to record the Lovenox injections on a log and return the form at the next study visit. A reminder call will be made to subjects the day before beginning each round of Lovenox. SQ Lovenox will not be required for subjects already taking an anticoagulant.

Subjects recruited from HSC-MS-16-0283 or HSC-MS-15-0744 will not be required to repeat the brain PET/DT-MRI for baseline imaging data.

3.6 Visits #3 thru 5: HB-adMSC Infusions

The infusion visits will be conducted in the CRU. Subjects will receive a total of 3 infusions (2×10^8 total cells per dose) administered over a 6 week period with 14 day intervals between infusions (+/- 3 days). The volume of each infusion will be 250mL infused over a 1hr. period (+/- 5 min.) at a rate of 4-5mL per minute.

At each infusion visit, the subject will undergo the following study procedures:

1. Interval H&P update (*detailed neuro exam if indicated from interview and physical exam, current medications and recent vaccinations*),
2. Confirmation the subject started prophylactic Lovenox injections and review of the Lovenox medication logs at follow-up visits,
3. A pregnancy test will be repeated for female subjects of child bearing potential (if applicable),
4. Vital signs (Heart Rate, BP, Resp., Temp., SpO₂),
5. Insertion of a peripheral IV line,
6. Blood sample for clinical labs (CBC with diff., CMP, coagulation and renal function panels),
7. Benadryl and Solumedrol will be given as pre-meds before the infusion. The dose for both drugs will be 25mg for subjects <100kg. or 50mg for subjects $\geq 100\text{kg}$.
8. A “time out” verification of patient/consent/procedure/cell product will be performed,

9. The HB-adMSC infusion will be given by through the peripheral IV,
10. The subject will then be monitored for a minimum of 4hr.

Vital signs will be continuously monitored during the infusion and recorded at 15 minute intervals. Vital signs will be recorded at the end of the infusion and then every 15 minutes x 4 (1st hour), and then every 30 minutes x 4 (next 2 hours), and then every hour until discharge from the CRU, or more frequently if clinically indicated. A chest x-ray may be obtained if clinically indicated to assess pulmonary AE/SAE's. The subject will be contacted by telephone 24hr. after each infusion visit to determine if adverse events have occurred. Each infusion visit is expected to take around 6 hours to complete.

